^e ECG should be done in triplicate (at screening, Day 1 and EOT visit) and allow rhythm definition (at least 30 seconds of duration), PR interval and QT interval (raw and corrected by HR using Bazett's formula). On Day 1, 5 minutes before SOI (-25 to -1 min before preinfusion PK samples collection) and 1 hour after EOI (-15 to -1 min before the PK sample collection), both will be done in triplicate.

^f A previous LVEF assessment could be used if was made within 28 days prior to screening and will be repeated if clinically indicated, and EOT.

^g Randomization apply for all patients.

^h Bosentan for self-administration and the patient's diary should be given to the patient on Day -6 with a $-2/+1$ day time window (i.e., from Day -8 to Day -5).

ⁱ Corticosteroids i.v. (according to institutional standard antiemetic doses, minimum dose of 8 mg/day and maximum dose of 20 mg/day of dexamethasone sodium phosphate or equivalent); If feasible, anti-emetic medication and dose administered in Cycle 1 should be maintained in Cycle 2. Serotonin (5-HT₃) antagonists (ondansetron at least 8 mg i.v. and no more than 16 mg of ondansetron) (i.e., 30 \pm 5 minutes before lubrinezdin administration).

^j If patient does not fulfill inclusion criteria (Cycle 1 in TR sequence) in Day 1 assessments and lubrinezdin administration is postponed no more than two days, bosentan should not be discontinued.

Study Period►	Screening (days prior to registration)	Cycle 1												Cycle 2					Cycle 3	End of Treatment	Follow-up AEs
		-6	-5	-4	-3	-2	-1	1*	2	3	5	8	15	1	2	3	5	8	15		
Cycle Day►																					

^k The study center will contact the patients (via telephone or other methods) to remind them or confirm that they have taken the morning and evening dose of bosentan when they are not at the study center.

^l Blood sample for genotyping will be collected at any time during the study but preferably just before infusion start in Cycle 1, only if written IC for the pharmacogenetic sub-study is given.

^m Serial peripheral venous blood samples for determination of lubinectedin (total and unbound), lubinectedin metabolites (i.e., M1 and M4) and bosentan plasma concentrations will be collected at the time points indicated in Section [8.1.1, Table 9](#).

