ⁿ Clinical assessment of the patient's signs and symptoms (including nurses' assessment and patient-reported issues) should continue on an ongoing basis throughout the study and be reported at least every cycle as AEs. Only information on SAEs that occurred after signature of the informed consent and up to Day -5 is required before treatment start. Grading should be as per the NCI-CTCAE v.5. Signs and symptoms will be assessed by the Sponsor as all the events ongoing during the screening period, except for prior history conditions, which should be reported in the medical history form. Ongoing events during the screening period are those present at any time between the informed consent date and the first drug administration, regardless of if they may be resolved or not at the date of Cycle 1 Day 1.

^o The "AE form" will be used only for events that occur after the first drug infusion or any event related to a study procedure within the study period (according to ICH guidelines); and to report 'ongoing' baseline conditions in case of any significant change (improvement or worsening) during the study.

^p Patients will be followed every four weeks until recovery to at least grade 1 or stabilization of all treatment-emergent AEs, or until the start of a new antitumor therapy, until the continuation of treatment outside this study under a Compassionate Use Agreement or death, whichever occurs first.

Hematology: Differential WBC (including neutrophils, monocytes and lymphocytes), erythrocytes, hemoglobin, hematocrit and platelets.

Coagulation: INR.

Biochemistry A: AST, ALT, AP, lactate dehydrogenase (LDH), creatinine, glucose, creatine phosphokinase (CPK), CPK-MB fraction (if CPK is elevated above the normal range) and gamma glutamyltransferase (GGT) and total bilirubin (direct bilirubin if total bilirubin is above the ULN).

Biochemistry B: Serum electrolytes (Na+, K+, Mg++), total calcium, total proteins, albumin, C-reactive protein (CRP).

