ⁿ Clinical assessment of the patient's signs and symptoms (including nurses' assessment and patient-reported issues) should continue on an ongoing basis throughout the study and be reported at least every cycle as AEs. Only information on SAEs that occurred after signature of the informed consent and up to Day -1 is required before treatment start. Grading should be as per the NCI-CTCAE v.5. Signs and symptoms will be assessed by the Sponsor as all the events ongoing during the screening period, except for prior history conditions, which should be reported in the medical history form. Ongoing events during the screening period are those present at any time between the informed consent date and the first drug administration, regardless of if they may be resolved or not at the date of Cycle 1 Day 1.

^o The "AE form" will be used only for events that occur after the first drug infusion or any event related to a study procedure within the study period (according to ICH guidelines); and to report 'ongoing' baseline conditions in case of any significant change (improvement or worsening) during the study.

^p Patients will be followed every four weeks until recovery to at least grade 1 or stabilization of all treatment-emergent AEs, or until the start of a new antitumor therapy, until the continuation of treatment outside this study under a Compassionate Use Agreement or death, whichever occurs first.

Hematology: Differential WBC (including neutrophils, monocytes and lymphocytes), erythrocytes, hemoglobin, hematocrit and platelets.

Coagulation: INR

Biochemistry A: AST, ALT, AP, lactate dehydrogenase (LDH), creatinine, glucose, creatine phosphokinase (CPK), CPK-MB fraction (if CPK is elevated above the normal range) and gamma glutamyltransferase (GGT) and total bilirubin (direct bilirubin if total bilirubin is above the ULN).

Biochemistry B: Serum electrolytes (Na⁺, K⁺, Mg⁺⁺), total calcium, total proteins, albumin, C-reactive protein (CRP).

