In case of lorbrena delay (≤ 2 days), bosentan could be administered twice daily during a maximum of seven consecutive days before lorbrena infusion, and supplied at the study center once daily on Day 1 (before lorbrena infusion).

All patients will receive a maximum of three cycles: two consecutive cycles of lorbrena, one cycle with and one cycle without bosentan co-administration (in different order depending on the study Sequence 1 or Sequence 2 of treatment), followed by a third cycle with lorbrena alone (this last optional for patients with clinical benefit). Patients will be randomized in a 1:1 ratio ([Figure 2](#)) to Sequence 1 (TR: Test- Reference; lorbrena + bosentan in Cycle 1) or Sequence 2 (RT: Reference-Test; lorbrena + bosentan in Cycle 2). Lorbrena will be administered as a 1-hour (-5/+20 min) intravenous (i.v.) infusion every three weeks (q3wk) via a central or peripheral vein. The dose of lorbrena will be 3.2 mg/m² for all patients when administered with and without bosentan. If toxicity occurs, the appropriate intra-patient dose level (DL) reductions will be implemented in the subsequent cycle. This DL reduction will be according to [Table 8](#).

Figure 2. Study design.

BOS, bosentan; LRB, lorbrena; TR, test-reference; R; randomized; RT, reference-test.

The enrollment of the patients will be simultaneous. However, if once the first three patients enrolled have completed Cycle 1 and Cycle 2, total lorbrena exposure does not allow an adequate PK assessment and if no unacceptable or life-threatening toxicities have occurred, the dose of lorbrena to be co-administered with bosentan in the remaining five patients can be adjusted accordingly.

This decision will be made by the Sponsor and the study Investigators. Therefore, the planned dose of lorbrena, when given with bosentan for the remaining five patients, will be based on the acceptability of the PK and safety results from the first three patients. If the initial three patients do not experience adverse events (AEs) which might require a dose-reduction, the dose of lorbrena may still be adjusted (based on the assumption of dose-proportional pharmacokinetics) to produce plasma lorbrena area under the curve (AUC) values that are comparable to those when lorbrena is given in the absence of bosentan. However, if toxicity occurs in the initial three patients, the appropriate dose-reduction of lorbrena will be implemented in the remaining five patients accordingly.

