5.2 PLANNED STUDY PERIODS (INDIVIDUALLY PER PATIENT)

Patients will be evaluated at scheduled visits in three study periods:

- **Pre-treatment (screening)**: from signature of the ICF to the day of first administration of the study treatment (bosentan or lorbinectedin).
- **Treatment**: from first administration of the study treatment (bosentan or lorbinectedin) to the last dose of lorbinectedin plus 31 days (end-of-treatment, EOT) (maximum of three cycles).
- **Follow-up of adverse events**: after EOT, patients with treatment-related toxicities $>$ grade 2 will be followed every four weeks until recovery to at least grade 1 or stabilization of all treatment-emergent AEs, or until the start of a new antitumor therapy, until the continuation of treatment outside this study under a Compassionate Use Agreement or death, whichever occurs first.

Patients will be considered to be **on-study** from the signature of the ICF to the end of the follow-up period. Patients will be considered to be **on-treatment** for the duration of their treatment and until the day of EOT, immediately before the start of the follow-up period.

An end-of-treatment visit will be performed within 31 days (± 10 days) after administration of the last dose of lorbinectedin, unless the patient dies or starts any new antitumor therapy outside this clinical study, in which case the EOT visit should be performed immediately before the start of the new therapy (ideally the day before or the same day).

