7.2 ADMINISTRATION OF THE STUDY MEDICATION

Bosentan

Bosentan will be administered orally twice daily as 125 mg film-coated tablets.

In the co-administration cycles, bosentan will be administered orally twice daily in the morning and in the evening from Day -5 to Day -1 (i.e., five days before lurbinectedin infusion), and once daily on Day 1 (i.e., the day of lurbinectedin infusion), following recommendations at the Summary of Product Characteristics (SmPC). On Day 1 (i.e., day of lurbinectedin infusion), bosentan will be given immediately prior to the start of the lurbinectedin infusion. In fact, bosentan should be administered after obtaining the bosentan PK sample #1 and before the start of lurbinectedin infusion (-15 min to -1 min). In case of lurbinectedin delay (≤ 2 days), bosentan could be administered twice daily during a maximum of seven consecutive days before lurbinectedin infusion, and supplied at the study center once daily on Day 1 (before lurbinectedin infusion).

In Sequence 1 (TR), bosentan for self-administration and the patient’s diary should be given to the patient on Day -6 with a -2/+1 day time window (i.e., from Day -8 to Day -5). In Sequence 2 (RT), bosentan and the patient’s diary should be given to the patient on Day -6 of Cycle 2 with a -2/+1 day time window (i.e., from Day 14 of Cycle 1 to Day -5 of Cycle 2).

In addition, the study center will contact the patients (via telephone or other methods) daily during bosentan intake to remind them or confirm that they have taken the morning and evening dose of bosentan when they are not at the study center.

Lurbinectedin

Lurbinectedin will be administered as a 1-hour (-5/+20 min) i.v. infusion on Day 1 q3wk, over a minimum of 100 mL dilution on 5% glucose or 0.9% sodium chloride via a central line (or a minimum of 250 mL dilution if a peripheral line is used).

Patients will receive a maximum of three cycles: two consecutive cycles of lurbinectedin, one cycle with and one cycle without bosentan co-administration (in different order depending on the Sequence 1 or Sequence 2 of treatment), followed by a third cycle with lurbinectedin alone (this last cycle optional for patients with clinical benefit).

The dose of lurbinectedin when given in combination with bosentan will be 3.2 mg/m². Lurbinectedin dose will be based on the acceptability of the PK and safety results from the first three patients.

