The “Adverse event form” will be used only for events that occur after the first drug infusion or any event related to a study procedure within the study period (according to ICH guidelines); and to report ‘ongoing’ baseline conditions in case of any significant change (improvement or worsening) during the study.

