9.1 ANALYSIS POPULATIONS

The PK population will include all patients enrolled who have sufficient and interpretable PK parameters to calculate the non-compartmental PK parameters. Only the patients who have completed the two cycles and have sufficient and interpretable PK assessments will be included in the statistical comparison to assess the effect of bosentan on the PK of lubrinezetin.

The safety population will include all patients who received at least one dose of lubrinezetin. Patients who have received at least one dose of bosentan but who did not receive any dose of lubrinezetin will be excluded from the safety population. The analysis of data from these patients will be performed separately (e.g., by means of narratives). The safety population will be used for all safety evaluations.

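### In Sequence 1 the adverse event form opens at the first lurbinectedin infusion although the adverse event period starts at the first bosentan dose, so new non-serious lead-in events may have no clearly assigned form

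*Protocol*

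**What the plan says.** **Where the form opens.** Protocol Section 8.5.1 restricts the AE form, which "will be used only for events that occur after the first drug infusion or any event related to a study procedure within the study period". It also allows the form for significant changes in ongoing baseline conditions. The rule is repeated in footnote o of both Schedules of Assessments and in footnote e of Table 5 (Section 6.4).

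**Where the AE period opens.** Section 5.2 and footnote d of Table 5 run the treatment period "from first administration of the study treatment (bosentan or" lurbinectedin), and the AE row of Table 5 uses that period. Footnote n of the Sequence 1 schedule reads: "Only information on SAEs that occurred after signature of the informed consent and up to Day -5 is required before treatment start". The matching Sequence 2 footnote says "and up to Day -1 is required before treatment start".

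**What must be recorded.** Section 8.5.1 also requires every AE to be entered in the source document and the eCRF, graded and related to each study drug. It defines signs and symptoms as events ongoing during screening. Section 5.2 ends screening on the day either drug is first given.

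**How bosentan is given.** It is an oral tablet taken twice daily from Day -5 to Day -1. On Day 1, "bosentan will be given immediately prior to the start of the" lurbinectedin infusion (Section 7.2). If the infusion is delayed by up to two days, "bosentan could be administered twice daily during a maximum of seven consecutive days before" it (Section 3.1).

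**The concern.** Two start points apply to the same data. One is the first dose of either drug. The other is the first infusion, which can only be lurbinectedin. In Sequence 2 the difference has no effect, because lurbinectedin is given first. In Sequence 1 the two points are separated by the whole bosentan lead-in, and footnotes n and o of the same schedule point in different directions.

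A site that follows the form rule would not open an AE form for, say, a new grade 2 headache on Day -3 of Sequence 1. For the same headache before Cycle 2 of Sequence 2 it would. A site that follows the on-treatment definition would open a form in both cases.

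The outputs exposed are those meant to show what bosentan adds: the BOS+LRB column of SAP Table 11.2.1.1, the bosentan-related table (11.2.1.4) and the listing of events related only to bosentan (11.2.1.10). They serve the secondary objective on the safety profile (Protocol Section 2.2).

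Patients who take bosentan but never receive lurbinectedin are also affected. Of these, Section 9.1 says: "The analysis of data from these patients will be performed separately (e.g., by means of narratives"). As planned they can arise only in Sequence 1, and for them the form would never open for a new non-serious, non-procedural event.

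**Working it through.** The plan gives no figure on this point, so there is none to reproduce. The check sets the boundaries side by side and counts the exposure between them.

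**Inputs**
- 8 patients allocated 1:1 (Protocol Section 9.2), taken as 4 per sequence.
- Lead-in of 5 days at 2 doses a day, plus 1 dose on Day 1 before the infusion (Sections 3.1 and 7.2).
- Maximum lead-in of 7 days under the permitted delay (Section 3.1). Sequence 1 schedule footnote j agrees: if lurbinectedin "administration is postponed no more than two days, bosentan should not be discontinued".

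**Boundaries**

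| Boundary | Sequence 1 | Sequence 2 |
|---|---|---|
| Signs and symptoms close (Sections 5.2 and 8.5.1) | First bosentan dose | Cycle 1 Day 1 lurbinectedin |
| On-treatment AE period opens (Section 5.2, Table 5) | First bosentan dose | Cycle 1 Day 1 lurbinectedin |
| AE form opens (Section 8.5.1, footnotes o and e) | Cycle 1 Day 1 lurbinectedin | Cycle 1 Day 1 lurbinectedin |
| Bosentan lead-in | Before the form opens | Before Cycle 2, after the form has opened |

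In Sequence 1 the first two boundaries coincide and the third comes later. The interval between them is the lead-in.

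**Size of the interval**
- Sequence 1 patient-days: 4 × 5 = 20, or 4 × 7 = 28 if all four have the full delay.
- Sequence 2 lead-in patient-days before the form opens: 0 of 20 (0 of 28).
- Both sequences together: 20/40 = 50%, or 28/56 = 50%, all of it in Sequence 1.
- Bosentan doses per Sequence 1 patient before the form opens: 5 × 2 + 1 = 11 of 11, or 7 × 2 + 1 = 15 of 15. In Sequence 2 the figure is 0 of 11.

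**The Day -5 cut-off.** The schedule defines Day 1 as the day lurbinectedin is actually given. With 7 days of bosentan before the infusion, the first dose falls on Day -7. A fixed Day -5 limit on the SAE-only window then comes 2 days after bosentan has started, so footnote n does not always mark the bosentan start either.

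**The case against.** The strongest reply is that Section 8.5.1 already requires all AEs in the source document and the eCRF, with a relationship to each drug. On that view the infusion wording governs only which form is used. This stands. A reader might infer that lead-in events would go unrecorded, and the documents do not support that. What remains is narrower: the general duty says record everything, the form rule says only after the infusion, and no other form is clearly named for the days in between.

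A second reply is that the signs-and-symptoms form would catch these events. SAP Listing 13.28 keeps the grade, onset date and relationship, so an event filed there could be reclassified by date. But signs and symptoms belong to screening, which in Sequence 1 ends at the first bosentan dose. SAP Section 10.2.9 would also place such events in baseline tables, not AE tables. The information may survive, but its place in the analysis is not assured.

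A reader might also infer that the protocol is unclear throughout about whether bosentan counts as study drug. That goes too far. The heading of Section 1.1 uses the term for lurbinectedin, but the Synopsis lists both products as study drugs, Section 8.4.6 gives reference safety information for both, and Appendix 2 calls bosentan an investigational product. The outlier is one repeated phrase about the first infusion. The undefined starting dose in the TEAE definition (Section 9.3.2) and in SAP Section 10.2.9 needs only to be tied to the same point.

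Finally, serious events are collected from consent (Section 8.5.2), and procedure-related events and significant changes in baseline conditions keep the AE form. The narratives for bosentan-only patients can also draw on source records. All of this is correct, and it limits the point to new, non-serious, non-procedural events.

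**Conclusion.** The inconsistency is real and should be fixed. Followed literally, the form rule leaves 20 planned Sequence 1 patient-days (28 at most), and every bosentan dose in that sequence, before the AE form opens. None of the Sequence 2 lead-in is in that position. Ascertainment of lead-in events can therefore differ by sequence and by site.

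The figures assume eight patients, four per sequence; replacement patients in Sequence 1 would add to them. They count days and doses, not events. The documents give no event rate for the lead-in, so neither the number of events affected nor any bias in the comparison can be estimated. It would be wrong to conclude that the safety comparison is biased; what is shown is that it may rest on uneven recording.

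The affected analyses are mainly descriptive; the only modelled safety comparison is the optional one in SAP Section 11.5. The pharmacokinetic primary endpoint is unaffected.

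**What to change.** 1. In Protocol Section 8.5.1, footnote o of both schedules and footnote e of Table 5, replace the infusion wording with: *after the first administration of bosentan or lurbinectedin, whichever is first*.
2. In footnote n of the Sequence 1 schedule, replace the Day -5 limit with: *up to the first administration of bosentan*. This also holds when the infusion is delayed.
3. Name the same point as the start of the TEAE definition (Section 9.3.2).
4. Name it also as the end of signs and symptoms: footnote n of both schedules, Table 4 footnote c, Section 8.5.1 and SAP Section 10.2.9.

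The cost is wording in the protocol and SAP, and perhaps a few more AE entries for about four patients. No visit, assessment or dosing rule changes.

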8.5.2 Reporting of Serious Adverse Events

The Sponsor will collect SAEs from the time of signing of the ICF and until 31 (± 10) days after administration of the last dose of lorbinecetin or until the start of a new antitumor therapy, until the continuation of treatment outside this study under a Compassionate Use Agreement or death, whichever occurred first. Beyond this period of time, only those SAEs suspected to be related to the IMPs will be collected. Nonetheless, the Sponsor must evaluate any safety information related to the clinical study that is spontaneously reported by an Investigator beyond the time frame specified in the protocol.

All SAEs (as defined above) that have occurred after patient registration, regardless of relationship to the study drug(s)/IMP(s), must be reported immediately, and always within 24 hours to the Pharma Mar S.A. Pharmacovigilance Department electronically by completing the applicable eCRF section. Only in situations of electronic system failure or pregnancy exposure during the clinical trial, can SAEs be reported using paper on a “SAE form by fax ([contact]), e-mail ([contact]@pharmamar.com) or telephone ([contact]). Out of office hours [Greenwich Meridian Time (GMT)], assistance on SAE reporting can be obtained by calling the Pharmacovigilance Department at [contact]. In case of electronic system failure or pregnancy exposure during the clinical trial, SAEs

initially reported by alternative methods (not electronically), must be followed by a completed electronic SAE reporting on eCRF from the investigational staff within one working day.

SAEs occurring during the screening phase (from ICF signature to the first study drug administration) and after off-study will be reported using a paper “SAE form” that must be forwarded as mentioned above always within 24 hours to the Pharma Mar S.A. Pharmacovigilance Department by fax or email.

All SAEs suspected to be related to the study drug must be followed until the event or its sequelae resolves or stabilizes to at least grade 1, or to an acceptable level according to the Investigator and the Sponsor or his/her designated representative.

